Official Title: Use of Leukocyte and Platelet-rich Fibrin Plasma (L-PRF) for the Prevention of Anastomotic Leakage in Colorectal Anastomosis

Document date: November 14th, 2017

November 14th, 2017

Study design

We will perform a randomized one blinded clinical trial with a total of 106 patients from the Surgical service of Hospital Guillermo Grant Benavente, in Concepción, Chile, submitted to elective colorectal anastomosis with mechanic anastomosis on or under the peritoneal reflection, with postoperative evaluation using contrast enema to objectify subclinical leak. Exclusion criteria will be age under 15 years, American Association of Anesthesiologists (ASA) grade IV or higher, clinical signs of peritonitis, other major surgeries within 30 days of the procedure, deficient nutritional state (defined by plasmatic albumin levels lower than 2.8 mg/dl), active treatment with corticoids and the impossibility of having contrast enema post-surgery.

Patients will be randomly assigned to experimental or control groups following a 1:1 ratio, by the team of surgeons the same day the surgical board was announced.

This study has been approved by the Ethical and Scientific Committee of Health Service of Concepción city. All participants will be explained their rights and were asked for their consent to enroll them in the study. On the other hand, anonymity and confidentiality of the participants will be assured during the study, as the patient's personal information was not included in the research database, which will be administered only by the main investigator and the statistical analyst.

This study will be held following the recommendations of Helsinki Declaration and World Medical Association.

Sociodemographic and clinical parameters

The following variables will be taken into account: (a) sociodemographic (age, gender); (b) clinical: body weight index (BMI), patient prognosis based on their comorbidities (ASA criteria, Charlson Score and preoperative albumin levels); (c) procedural: indication (oncologic, transit reconstruction, volvulus, sigmoid fistula, dolico-colon), type of surgery (sigmoidectomy, anterior rectal resection, reconstruction), drainage (yes or no), surgical approach route (open, laparoscopic); (d) main outcomes: surgical complications (Clavien-Dindo classification), anastomotic dehiscence (yes or no), hospitalization days and mortality.

Surgical intervention

L-PRF will be obtained from a blood sample from each patient in the experimental group through Vacutainer® system, using a sterile, double-ended needle, with a retractable sleeve that allows multiple samples to be taken, and collector tubes without additives. About eight blood tubes will be collected for each patient, with a maximum extraction of 80cc. Samples will be centrifuged for 12 min at 2700 rpm obtaining 3 phases; a lower fraction of red blood cells, a middle one with fibrin clots and the supernatant containing exudate without plasma.

Once the preparation is obtained, the fibrin clot will be extracted in aseptic conditions, and crushed for 5 min with a pressure that does not exceed 80 milligram, using a pre-designed device with the appropriate weight (PRF-kit).

Finally, the L-PRF membranes will be put over the anastomotic zone, after the exteriorization of the circular stapler punch, with full coverage of the region, leaving the membranes in contact with the bloody zone of anastomosis. For open surgery, L-PRF membranes will be put manually and for laparoscopic surgery, they will be introduced by a 12mm trocar and positioned with laparoscopic forceps.

Postoperative outcomes

Anastomotic leak will be defined as a communication between intraluminal and extraluminal compartments due a defect in the intestinal wall anastomosis. An abscess in the proximity of the anastomosis and leakage of extraluminal contrast enema was considered an anastomotic leak.

Invasive treatment of surgical complications will be defined as any invasive procedure performed after the primary surgery, including radiological drainage.

Complications that required re intervention or anastomosis removal, hospitalization days, including hospital re admissions due adverse events, and mortality will be also considered in the analysis.

Data collection

Data will be registered by general surgery and coloproctology residents previously trained by the main investigator. To assure the validity of the registry, tabulations will be performed by two residents independently, being later contrasted. For the data registry Microsoft Excel 2011 version will be used.

Statistical analysis.

An exploratory analysis of the data will be performed by calculating averages and standard deviations, along with absolute and relative frequencies. For comparing quantitative variables in two independent samples, Mann Whitney U test will be used. On the other hand, to study the association between two nominal variables with two categories, Fisher exact test and the Chi-square test of independence will be used. The significance level will be set in a p value $\leq 0,05$. Stata 14.0 will be used as the statistical analysis software.

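### The level of the anastomosis defines who is eligible, but it is not a listed variable, an allocation factor or an analysis factor

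*Combined protocol and SAP*

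**What the plan says.** All references are to the combined protocol and SAP.

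- **Study design.** The trial enrols "a total of 106 patients" having elective surgery with a "mechanic anastomosis on or under the peritoneal reflection". Both positions qualify.
- **Study design, allocation.** Patients are "randomly assigned to experimental or control groups following a 1:1 ratio, by the team of surgeons". No block, stratum or minimisation factor is named.
- **Sociodemographic and clinical parameters.** The procedural variables are indication and "type of surgery (sigmoidectomy, anterior rectal resection, reconstruction), drainage (yes or no), surgical approach route (open, laparoscopic"). Age, gender, BMI, ASA, Charlson score and albumin are also listed. There is no height from the anal verge and no field for position relative to the reflection. The leak outcome is "anastomotic dehiscence (yes or no").
- **Statistical analysis.** For two-category variables, "Fisher exact test and the Chi-square test of independence will be used". No stratified or adjusted comparison is planned.

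**The concern.** Level is the trial's one positive anatomical entry criterion, and the plan makes no provision to capture it. Two consequences follow.

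The first needs no assumption about risk. Without the field, the dataset cannot confirm that an analysed patient was eligible. A reader also cannot tell to which level the result applies, or whether the arms were alike in this respect. Type of surgery does not fill the gap: it names the operation, not where the join lies, and a reconstruction may fall at either level. No adjustment for type of surgery is planned either.

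The second depends on leak risk differing by level, which the documents do not state. If it does, a chance excess of low anastomoses in one arm would shift the observed leak difference, and could resemble or mask an L-PRF effect. Neither the allocation nor the analysis guards against this.

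**Working it through.** The plan gives no figure to reproduce: 106 is stated without leak rates, effect size or power. The check therefore sizes the issue under stated assumptions.

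**Inputs from the document.** 106 patients at 1:1, so 53 per arm; p ≤ 0.05; chi-square or Fisher on a two-by-two table.

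**Assumptions.** 40% of patients below the reflection (30% and 50% also tried). Leak risk 10, 15 or 20 points higher below than at it: 19% v 9%, 22.5% v 7.5%, 26% v 6%. The overall risk is then 13% to 14%; for example, 0.40 × 26% + 0.60 × 6% = 14%. For power, a leak risk ratio of 0.35 at both levels.

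**Step 1: chance imbalance with 53 v 53.** If K of the 106 are below the reflection and x of them fall in one arm, x is hypergeometric and the imbalance is |2x − K|/53.

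| Share below | K | ≥10 points | ≥15 points |
|---|---|---|---|
| 30% | 32 | 29% | 14% |
| 40% | 42 | 32% | 16% |
| 50% | 53 | 24% | 12% |

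The figures jump because x is a whole number: at K = 42, 15 points means 8/53 = 15.1%. Letting K vary (each patient below with probability 40%) gives 13-14% for 15 points or more.

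**Step 2: shift in the leak-risk difference.** Shift = imbalance × gap between levels. The smallest case is 0.10 × 10 points = 1 point. A 15-point imbalance with a 20-point gap gives 0.15 × 20 = 3 points.

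**Step 3: error rate with no L-PRF effect.** 40,000 simulated trials per row, 53 v 53, K varying.

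| Gap | Chi-square, all trials | Chi-square, imbalance ≥15 | Mantel-Haenszel by level, imbalance ≥15 |
|---|---|---|---|
| 10 points | 4.8% | 5.3% | 4.8% |
| 15 points | 4.8% | 6.8% | 5.0% |
| 20 points | 4.9% | 7.3% | 5.0% |

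The conditional columns rest on about 0.136 × 40,000 ≈ 5,400 trials, so their standard error is about 0.3 points. If allocation were instead an independent coin toss for each patient, the conditional chi-square figure at the 20-point gap is 7-8%.

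**Step 4: power at a risk ratio of 0.35.** K = 42; stratified allocation splits each level equally (21/21 and 32/32).

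| Gap | Unstratified, chi-square | Unstratified, Mantel-Haenszel | Stratified, Mantel-Haenszel |
|---|---|---|---|
| 10 points | 33.3% | 33.4% | 34.8% |
| 15 points | 34.6% | 35.1% | 37.0% |
| 20 points | 35.7% | 36.9% | 38.4% |

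Stratifying both allocation and analysis gains 1.5, 2.4 and 2.7 points. Stratifying the analysis alone gains about 0 to 1 point.

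**The case against.** Unstratified 1:1 randomisation is a legitimate design. It balances level on average, and the planned tests are valid over all randomisations. The conditional inflation belongs to an unlucky minority of trials and would appear for any prognostic variable. The plan also names Fisher's test, which is conservative here: at the 20-point gap, given an imbalance of 15 points or more, its error rate is about 4% with 53 v 53 and just under 6% with coin-toss allocation. The power gain is small, and neither design is well powered at the assumed effect. Planned level will sometimes differ from final level; the simulation ignores this, so the gain shown for stratified allocation is an upper figure. All of this stands and limits the size of the point. It does not supply the missing field.

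Two stronger readings are tempting, and the documents support neither.

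- A reader might infer that imbalance in level can be neither prevented, seen nor corrected. The text shows only that level is not a listed variable or a planned factor. It may well be recoverable from operative notes, although the plan makes no provision for that.
- A reader might infer that silence about blocks means coin-toss allocation, and so unequal arm sizes. The section gives only the ratio and who allocates. The method is unstated, so the main figures above use fixed arms of 53.

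**Conclusion.** The point holds as a cheap improvement, not as a threat to the trial's validity. Level defines the population yet is absent from the variable list, the allocation and the analysis. The planned dataset therefore cannot show eligibility or balance by arm, and chance imbalance is not controlled by design. That conclusion rests on the text alone.

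The size of the statistical effect depends on leak risk differing by level. Over assumed gaps of 10 to 20 points it is modest: overall error stays near 5%, the conditional chi-square error ranges from barely above 5% at the smallest gap to about 7%, and stratifying both allocation and analysis is worth about 1 to 3 points of power. The main gain is a dataset in which eligibility and balance can be checked and a chance imbalance corrected by a method fixed in advance.

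**What to change.** 1. **Variables.** Add to the procedural list the height of the anastomosis from the anal verge (cm) and whether it lies at or below the reflection. Report both by arm.
2. **Analysis.** Compare leak with a Mantel-Haenszel test (no continuity correction, as in the working) and a Mantel-Haenszel risk difference, stratified by level. Keep Fisher and chi-square as supporting analyses.
3. **Allocation, where feasible.** Have the statistical analyst prepare one list per planned level, in permuted blocks of varying size, and use that planned level as the analysis stratum. Planned level is fixed before the arm is known. Final level is set at operation, after a surgical team that does the allocating may know the arm.

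**Cost.** One extra data field (two entries), one line in the analysis section and, if item 3 is adopted, two lists instead of one. Planned level must be written down before allocation and will sometimes differ from the final level; patients stay in the stratum in which they were allocated. The gain is modest, so items 1 and 2 are the minimum and item 3 is desirable.

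### Hospitalization days is compared without the baseline prognostic variables the trial collects; the unadjusted test is valid but may give up some power

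*Combined protocol and SAP*

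**What the plan says.** The section on sociodemographic and clinical parameters lists the variables to be considered. The clinical ones include "patient prognosis based on their comorbidities (ASA criteria, Charlson Score and preoperative albumin levels". The procedural ones include "surgical approach route (open, laparoscopic". The same section names four main outcomes: complications, anastomotic dehiscence, hospitalization days and mortality. None is singled out as primary.

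The Statistical analysis section is one paragraph. For quantitative outcomes it says: "For comparing quantitative variables in two independent samples, Mann Whitney U test will be used". For two-category outcomes it names the Fisher exact and Chi-square tests. It contains no regression, analysis of covariance or stratified test, and the plan never says how the listed baseline variables will enter the comparison of arms.

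The Study design section describes a "randomized one blinded clinical trial with a total of 106 patients". On allocation it says: "Patients will be randomly assigned to experimental or control groups following a 1:1 ratio, by the team of surgeons". It names no stratification factor.

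**The concern.** The protocol itself describes three of the recorded baseline variables as measures of prognosis. If such a variable predicts length of stay, adjusting for it removes outcome variation that has nothing to do with the intervention, so the same 106 patients can detect a smaller difference. The plan uses these variables neither in the allocation nor in the analysis.

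Two things are at stake. The first is power for hospitalization days, where every patient contributes a quantitative value and adjustment is feasible at this sample size. The second is pre-specification: an adjusted analysis added after the outcomes are known would be open to the charge that its covariates were picked for the result.

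**Working it through.** **Inputs from the documents.** There are 106 patients allocated 1:1, so 53 per arm. The significance level is 0.05; sidedness is not stated and two-sided is assumed. The planned test is the unadjusted Mann-Whitney. The documents give no standard deviation for stay, no expected effect, no power and no prognostic strength for any covariate, so the plan has no power figure to reproduce.

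**Assumptions.** Stay is lognormal with log-SD 0.5. The true effect is a 25% shorter stay. The covariate explains a share R² of the variance of log stay, varied from 0 to 0.3.

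**Step 1: unadjusted power by hand.** The effect on the log scale is −ln(0.75) = 0.288. Its standard error is 0.5 × √(2/53) = 0.0971, so z = 0.288/0.0971 = 2.96. The Mann-Whitney test has efficiency 3/π = 0.955 relative to the t test on normal data, so z becomes 2.96 × √0.955 = 2.89. Power is Φ(2.89 − 1.96) ≈ 0.82. Simulation gives 0.81 to 0.82, in agreement.

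**Step 2: what one covariate does to the variance.** The approximate ratio of adjusted to unadjusted variance, with one covariate and N = 106, is (1 − R²) × 103/102. Effective sample size is 106 divided by that ratio.

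| R² | Variance ratio | Effective N |
|---|---|---|
| 0 | 1.010 | 105 |
| 0.05 | 0.959 | 110 |
| 0.1 | 0.909 | 117 |
| 0.2 | 0.808 | 131 |
| 0.3 | 0.707 | 150 |

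Break-even is at R² = 1 − 102/103, about 0.01.

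**Step 3: simulated power.** The setting is 53 per arm, log-SD 0.5 and a 25% shorter stay.

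| R² | Mann-Whitney | Rank ANCOVA, one Charlson-like score |
|---|---|---|
| 0 | 81–82% | 81% |
| 0.1 | 81–82% | 84% |
| 0.2 | 81–82% | 87% |
| 0.3 | 81–82% | 91% |

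Type I error of the rank ANCOVA stayed near 5%. A run with two covariates (3,000 trials per cell) filled in the weak end: 82.2% unadjusted against 81.8% adjusted at R² 0, 81.5% against 81.9% at 3%, 81.5% against 82.2% at 5%, and 81.5% against 84.3% at 10%.

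**Step 4: sensitivity to the assumed spread.** With log-SD 0.7 the standard error is 0.7 × √(2/53) = 0.136, z = 0.288/0.136 × √0.955 = 2.07, and unadjusted power is Φ(2.07 − 1.96) ≈ 0.54. Simulation gives about 54% unadjusted and 57% adjusted at R² 10%. The absolute powers therefore depend on the assumed spread, while the gain at R² 10% is again about 3 points.

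**Step 5: leak.** Unstratified 53/53 allocation gives a probability of 0.12 that a factor present in 50% of patients differs between arms by 15 points or more (hypergeometric). If leak differed by 10 points between open and laparoscopic surgery (assumed), a 15-point imbalance would move the arm difference by 0.15 × 10 = 1.5 points. The standard error of that difference is √(2 × 0.10 × 0.90/53) = 5.8 points at 10% leak and √(2 × 0.15 × 0.85/53) = 6.9 points at 15%. The shift is small beside either. Power for leak does not improve reliably: in simulations adjusting for four covariates by a linear model, with leak of 20% against 5%, adjusted power was 67%, 68% and 71% at R² 0, 0.07 and 0.17, against 67 to 69% for Chi-square. At 10% against 2%, about six leaks in all, a logistic model with those covariates separated or failed to converge in 43 to 47% of trials.

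**The case against.** The strongest reply is that nothing here is invalid. Randomisation, if properly carried out, balances covariates in expectation, and the unadjusted tests already allow for chance imbalance in their type I error. That stands. A reader might infer that the plan has no protection against imbalance, and the documents do not support that. What is missing is correction for the particular imbalance that arises, and some power.

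A second reply is that the gain is not shown to be large. That also stands. The documents give no prognostic strength, and the exclusions of "American Association of Anesthesiologists (ASA) grade IV or higher" and of "deficient nutritional state (defined by plasmatic albumin levels lower than 2.8 mg/dl" narrow the range of two of the candidate covariates. Calling the precision free would overstate it: if the covariate is uninformative, adjustment costs a little, and below about 5% of variance explained the gain is negligible.

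A third reply is that surgical approach may not be usable. It is listed with the procedural variables, and nothing says whether the planned or the performed route is recorded. If it is the performed route, it may reflect events after allocation. So one cannot say that every covariate one might want is already collected. Charlson score does not share this difficulty.

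Finally, the trial is about preventing leak, and hospitalization days is one of four main outcomes. This limits the weight of the point but does not remove it, because the change is small and the loss if it proves unnecessary is at most about one point of power.

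**Conclusion.** The point holds as a modest improvement confined to hospitalization days. The protocol collects prognostic baseline variables, and its planned test for that outcome ignores them. With log-SD 0.5 and a 25% shorter stay, both assumed, rank ANCOVA on one baseline score adds about nothing at R² 0 to 5%, about 3 points of power at 10%, and about 6 to 9 points at 20 to 30%. Type I error stays near 5%, and the worst-case cost is about one point. Neither the absolute powers nor the R² values are properties of this trial; they show the range.

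A reader might also infer that leak should be adjusted for precision. The figures do not support this: the gain is small or absent at plausible event counts, and a multivariable logistic model can be unstable. A stratified check on leak would be a robustness analysis only.

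**What to change.** In the Statistical analysis section, name the main comparison for hospitalization days as a rank ANCOVA: rank stay over all patients, rank Charlson score with mid-ranks for ties, and regress the ranked stay on arm and ranked Charlson score. Report the unadjusted Mann-Whitney test beside it. Add surgical approach as a second covariate only if the route planned before randomisation is recorded. Fix this text before any outcome data are examined.

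For leak, keep an unadjusted test as primary. An exact Mantel-Haenszel comparison stratified by planned approach may be listed as an optional sensitivity analysis.

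The cost is two or three lines of text and a few lines of code in the Stata version already chosen. Charlson score is already on the list of variables. Planned approach may need a new data item, so the sponsor should confirm what is recorded before relying on it.

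### Does naming both Fisher's exact test and chi-square for leak, with no rule for choosing between them, leave the trial's result undefined?

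*Combined protocol and SAP*

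**What the plan says.** The Statistical analysis section sets out one approach for all binary comparisons. It is meant "to study the association between two nominal variables with two categories", and for these "Fisher exact test and the Chi-square test of independence will be used". The threshold follows: "The significance level will be set in a p value" of at most 0.05. Sidedness, an expected-count condition and a continuity correction are not mentioned. Leak is not named there, but the section on sociodemographic and clinical parameters lists anastomotic dehiscence as a yes/no item among the main outcomes, so it falls under this sentence. So do gender, drainage, surgical approach and mortality.

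Study design describes a trial "with a total of 106 patients", allocated to "experimental or control groups following a 1:1 ratio" and assigned "by the team of surgeons the same day the surgical board was announced". No blocking is described, so arms of exactly 53 and 53 are intended but not assured.

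**The concern.** Leak prevention is the purpose in the trial's title. Read literally, the plan produces two p-values for it and does not say which one counts. The two tests can fall on different sides of 0.05 for the same table, and a continuity correction can move chi-square across the line as well. If the choice were made after seeing the table, one might fear selective quotation of the favourable p-value. If Fisher were the one to decide, some power would be lost in a trial of only 106 patients.

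**Working it through.** **Inputs.** From the document: 106 patients, 1:1, yes/no leak, threshold 0.05. Assumed because the document does not give them: two-sided tests; simple randomisation; ten pairs of leak rates (10/5, 20/10, 15/5, 20/5, 15/3, 10/2, 12/2, 25/10, 25/5 and 30/5%). The plan gives no power figure, so there is none to reproduce.

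**Step 1: can the calls differ?** Take 3 of 53 vs 10 of 53 leaks, so 13 leaks and 93 non-leaks.

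- Uncorrected chi-square: 106 × (3×43 − 10×50)² / (53×53×13×93) = 106 × 371² / 3,396,081 = 4.30, p = 0.038.
- With continuity correction: 106 × (371 − 53)² / 3,396,081 = 3.16, p = 0.076.
- Fisher, two-sided: p = 0.072.

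So they can differ.

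**Step 2: how often?** All tables were enumerated and weighted by the product of two binomial distributions. At exactly 53/53, uncorrected chi-square and Fisher differ with probability 3.2% to 19.3% over the ten pairs. Exactly 53/53 has only 7.7% probability under simple randomisation. Averaged over splits from 43/63 to 63/43 (95.9% of the probability), the range is 1.8% to 11.3%; it is 6.7% at 20% vs 5% and 11.3% at 10% vs 2%.

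**Step 3: does the looseness inflate false positives?** At no split in that range is there a table with Fisher significant and uncorrected chi-square not. A continuity correction only shrinks the statistic, so corrected rejections are also uncorrected ones. Quoting the most favourable of the three is therefore the same as using uncorrected chi-square. Its maximum size is 5.3% at 53/53 and 5.6% at the worst splits (46/60 and 49/57).

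Exact size at 53/53, common leak rates of 5% to 30%:

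| Test | Size |
|---|---|
| Fisher | 0.8–3.0% |
| Corrected chi-square | 0.8–3.0% |
| Uncorrected chi-square | 4.4–5.3% |
| Expected-count rule | 1.1–5.3% |

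**Step 4: what does the usual reading give?** The expected-count rule uses uncorrected chi-square when the smallest expected count is at least 5, and Fisher otherwise. For 3 vs 10 at 53/53 the smallest expected count is 53×13/106 = 6.5, so chi-square decides. For 1 vs 7 it is 53×8/106 = 4.0, so Fisher decides (p = 0.060; chi-square would give 0.027). Each table gets one call.

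Average power over splits:

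| Assumed rates | Expected-count rule | Uncorrected chi-square | Difference (points) |
|---|---|---|---|
| 20% vs 5% | 65.9% | 67.5% | 1.6 |
| 25% vs 10% | 53.7% | 53.8% | 0.1 |
| 20% vs 10% | 29.8% | 30.2% | 0.4 |
| 10% vs 2% | 30.8% | 41.5% | 10.7 |

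**The case for a change.** The strongest case for a change is that the expected-count rule is nowhere written, that leak is the titled outcome, and that one or two sentences before outcome data are seen would settle the matter. The usual rule also leaves the continuity correction open: in the 3 vs 10 table it selects chi-square, whose p-value is 0.038 or 0.076 depending on that choice. At 52/54, Fisher can be significant where corrected chi-square is not, with probability up to 13.6%. If Fisher alone decided, average power at 20% vs 5% would be 60.8% rather than 67.5%.

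The textual gap stands, and writing the rule down would be tidy. The inference that the result is therefore unsound does not. In a split table both tests see the same data, direction and effect, and differ only in where a borderline p-value lands; these are not opposite findings. Every candidate choice keeps the false-positive rate at 5.6% or below.

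Going further and naming uncorrected chi-square alone gains power mainly at low leak rates and accepts a size that can exceed 5%, which Fisher's cannot. A team that prefers Fisher or the expected-count rule is not in error.

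**Conclusion.** No change is called for. The plan omits a detail that analysts ordinarily supply: choose by expected counts, one call per table. Under that reading power is within 1.6 points of uncorrected chi-square at the three moderate-rate pairs tabulated, and falls clearly behind (10.7 points) only at the low pair of 10% vs 2%. Under the loosest reading, borderline tables get differing significance calls in about 2% to 11% of trials on average, with size no higher than 5.6%.

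The split and power figures rest on assumed leak rates, and the averages also on simple randomisation, because the document states neither. All figures assume two-sided tests. The size bound does not depend on the ten assumed pairs: it was searched over common rates of 0.2% to 50% at every split from 43/63 to 53/53. Which single test is best is a fair trade-off between power and strict control at 5%.
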